11.2.2. Exploratory Predictive p-ERK Analyses

The objective of the statistical analysis outlined in this section is to characterize potential of p-ERK to be a predictive biomarker assessed from tumor tissue and biological response as measured by changes in tumor volume.

11.2.2.1. Change from baseline

Depending upon data availability, exploratory analyses may be performed to examine potential relationships between decrease from baseline H-score from tumor biopsies, and tumor response.

Tumor response will be quantified using change from baseline of tumor measurements (% change sum of lesion diameters [SLD]). Percent change from baseline for sum of lesion diameters is set to missing if any target lesions at baseline are missing or not measured at post baseline observation. Correlation between decrease in H-score and %SLD will be evaluated using Spearman's correlation coefficient. A scatter plot will be created for each treatment arm.

Summaries of the relationship between change in H-score and CR/PR/ Stable Disease (SD)/ Progressive Disease (PD) (without confirmation) will be assessed if data permit (i.e. if there are enough subjects with CR, PR etc.).

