- 5. Baseline MRI (preferred) or CT (only if MRI contraindicated or unavailable) of the brain must be performed on all patients to rule out current leptomeningeal metastases, brain metastases, or spinal cord compression secondary to metastasis. Post-baseline scans should be performed in all patients with documented metastases at baseline and as clinically indicated (e.g., symptoms suggestive of CNS progression) in all patients.
- 6. Lesion assessments must be done for chest, abdomen, pelvis, and any area of known disease. Lesion assessment by contrast CT (preferred) or MRI must be performed within 5 weeks prior to randomisation and at the times indicated until disease progression, death, or withdrawal of consent, whichever occurs first. (See Section 7.3.3 for instructions regarding chest X-Rays and CT assessment.) Target and non-target lesions must be identified at the time of screening and the same lesions must be re-assessed at each timepoint in a consistent manner according to RECIST, version 1.1. The same diagnostic method, including use of contrast when applicable, must be used throughout the study to evaluate each lesion. Lesion measurements will be taken using ruler or calipers. The Week 8 assessment for patients in arms A & B should be done before starting the combination treatment. If the last assessment was > 8 weeks prior to study withdrawal and disease progression had not been documented, a disease assessment should be obtained.

- 7. Randomisation will occur via RAMOS on Day 1.
- 8. Refer to Section 7.4.6 for details regarding vital sign measurements.
- 9. A complete physical examination will be performed at Screening and End-of-study; brief physical examinations will be performed at all other timepoints as indicated. In females, genitourinary exam should include a visual inspection of the cervix. If the patient has had a genitourinary and rectal exam within 6 months of screening the genitourinary and rectal exam do not need to be repeated. Refer to Section 7.4.7 for details.
- 10. An ophthalmic examination will be performed at Screening; additional ophthalmic examinations will be performed only as symptomatically warranted. Refer to Section 7.4.5 for details.

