11.2. Investigator Assessment of H-Score

The primary endpoint analysis will be the evaluation of the percentage change of the mean Phosphorylated Extracellular Signal-regulated Kinase (p-ERK) H-Score from baseline. At the beginning of IP treatment, the p-ERK H-Score will be determined for all participants in the biomarker population.

Change in biomarker status is most prominent within two weeks of start of treatment. Patients from arm A and arm B will be given combination therapy starting from week 9 after completion of 8 weeks of monotherapy. Therefore, changes in biomarker between screening and week 2 as well as between week 8 and week 10 will be summarized and listed. All visits for biomarker samples have a window of ± 7 days.

More specifically, the procedure for calculating the p-ERK score is shown below:

- Intra-tumoral expression levels of ERK, a tumor tissue biomarker, will be measured using immunohistochemistry methods that incorporated both intensity and distribution of staining. A value designated the H-Score will be derived by summing the percentages of cells staining at each intensity multiplied by the weighted intensity of staining (0, 1+, 2+, 3+: 3+ indicates the strongest staining, 2+ indicates medium staining, 1+ indicates weak staining, and 0 indicates no staining). H-Scores range from a minimum score of 0 to a maximum score of 300; the maximum score indicates the strongest expression. We will also collect a summary staining score for the tumor tissue which has potential values of 0 (no staining), 1+ (weak staining), 2+ (medium staining), and 3+ (strong staining).

$$\begin{aligned}
 H - Score &= (3 * \% \text{ Cells with strongest staining}) \\
 &\quad + (2 * \% \text{ Cells with medium staining}) \\
 &\quad + (1 * \% \text{ Cells with weak staining}) \\
 &\quad + (0 * \% \text{ Cells with no staining}) \uparrow
 \end{aligned}$$

All p-ERK H-Score data will be recorded on the eCRF, including data on % positivity for all participants in the biomarker population, which is calculated using the equation below:

$$\begin{aligned}
 \% \text{ Positivity} &= \% \text{ of cells with weak staining} \\
 &\quad + \% \text{ of cells with medium staining} \\
 &\quad + \% \text{ of cells with strong staining} \uparrow
 \end{aligned}$$

Summary statistics, graphics, and statistical modeling will be conducted on the biomarker population for each arm of the study.

11.2.1. Primary p-ERK Biomarker Analyses:

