Analyses from this section will utilize p-ERK H-scores from pre-dose, 2-week, 8-week, and 10-week biopsies. Summary statistics (mean, standard deviation, median, minimum, and maximum) will be reported at each time point and for change (actual and percent

changes) from baseline to two weeks in Arm C and for change from 8-week and 10-week in Arms A and B for p-ERK using H-score values.

Depending upon data availability, \log_2 -transformed values of p-ERK H-Score results will be analyzed by analysis of variance (ANOVA) for each cohort. In some cases, it is possible for p-ERK H-Scores to have a value of zero, and if these zero H-Scores are present in the data, we will add an offset of one to all values before conducting any \log_2 -transformations. This analysis will consider time and treatment as the fixed effect, and subject as a random effect. The H-Score calculation at either screening (analysis for combo arm) or week 8 (analysis from monotherapy arms) is the test comparison and the H-Score calculation at either week 2 (analysis for combo arm) or week 10 (analysis from monotherapy arms) is the reference calculation. The analysis will be performed using the mixed linear models procedure within the SAS/STAT module of the SAS system. Point and $(1-2\alpha^*)$ interval estimates of the difference in least-square (LS) means of the test less the reference treatment will be derived using SAS code such as that described below:

```
proc mixed;  
class trt time subject;  
model HScore = time trt;  
random subject;  
lsmeans trt;  
estimate 'B vs. A' trt -1 1 / cl alpha=0.05  
run;
```

(In this code, trt, HScore, and time refer to treatment given, H-Score Value, and the time of H-Score analysis, respectively).

For each primary endpoint, results from these analyses will be exponentiated to obtain point and 90% confidence interval estimates of the appropriate test to reference ratios of geometric least-squares (GLS) means.

Assumptions underlying these analyses will be assessed. If the assumptions are seriously violated, then nonparametric methods will be considered.

The mean and median Intra-tumoral expression levels of ERK over time will be plotted, with treatment highlighted using appropriate graphical techniques (e.g. trellis, plotting symbol, and colour).

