5.0091	Multivariate Proportional Cox Model Examining the relationship between H-Score and Duration of Response for patients with BRAF V600E mutation	Biomarker		See HScore5 Mock-Up	Display is built off of the immunogenicity display IMM2	SAC
5.0100	Correlation of Changes in H-Score after Two Weeks of Combo Therapy and Changes in Tumor Burden	Biomarker		See HScore6 Mock-Up	Will contain the clinical marker of interest, Treatment Arm, Spearman's Coefficient, and Sample Size (N)	SAC
5.0110	Correlation of H-Score and Changes in Tumor Burden	Biomarker		See HScore6 Mock-Up	Will contain the clinical marker of interest, Treatment Arm, Spearman's Coefficient, and Sample Size (N)	SAC
5.0120	Summary of Investigator-Assessed Best Response without confirmation per percentage change category in H-Score (Using RECIST 1.1. criteria)	Biomarker		See HScore7 Mock-Up	Display is built off of the oncology response display RE1a	SAC

CONFIDENTIAL

BRF116613

Table No.	Title	Population	Component / Therapeutic Area (hyperlinked to IDSL LN DB)	IDSL No. or Example Shell No.	Study-Specific Display Notes	Deliverable Priority
5.0130	Summary of Investigator-Assessed Best Response without confirmation per baseline H-Score category (Using RECIST 1.1. criteria)	Biomarker		See HScore8 Mock-Up	Display is built off of the oncology response display RE1a	SAC

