18.1.5.2. Figures

Figure No.	Title	Population	Component / Therapeutic Area (hyperlinked to IDSL LN DB)	IDSL No. or Example Shell No.	Study-Specific Display Notes	Deliverable Priority
15.0010	Mean p-ERK Scores – Time Plot (Linear and Semi Log)	Biomarker		PK17	Replace Concentration (ng/mL) with H-Score on the y-axis, and have maximum value as 300. Replace Planned Relative Time (Hours) with Planned Screening Time (Weeks) for the x-axis and have values (0, 2, 8, and 10)	SAC
15.0011	Mean p-ERK Scores – Time Plot (Linear and Semi Log) for patients with BRAF V600E mutation	Biomarker		PK17	Replace Concentration (ng/mL) with H-Score on the y-axis, and have maximum value as 300. Replace Planned Relative Time (Hours) with Planned Screening Time (Weeks) for the x-axis and have values (0, 2, 8, and 10)	SAC
15.0020	Median p-ERK Scores – Time Plot (Linear and Semi Log)	Biomarker		PK17	Replace Concentration (ng/mL) with H-Score on the y-axis, and have maximum value as 300. Replace Planned Relative Time (Hours) with Planned Screening Time (Weeks) for the x-axis and have values (0, 2, 8, and 10)	SAC
15.0021	Median p-ERK Scores – Time Plot (Linear and Semi Log) for patients with BRAF V600E mutation	Biomarker		PK17	Replace Concentration (ng/mL) with H-Score on the y-axis, and have maximum value as 300. Replace Planned Relative Time (Hours) with Planned Screening Time (Weeks) for the x-axis and have values (0, 2, 8, and 10)	SAC
15.0030	Scatter plot for Correlation between Changes in H-Score after Two Weeks of Combo Therapy and Changes in Tumor Burden	Biomarker		See HScore9 Mock-Up	Have a different color and symbol for each drug cohort. Y-axis contains %SLD information and x-axis contains change in H-Score information. Example is for illustrative purposes only and does not represent real data.	SAC
15.0040	Scatter plot for Correlation between Baseline Changes in Tumor Burden	Biomarker		See HScore9 Mock-Up	Have a different color and symbol for each drug cohort. Y-axis contains %SLD information and x-axis contains baseline H-Score information. Example is for illustrative purposes only and does not represent real data.	SAC

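### In Arms A and B, the displays for SAP 11.2.2.1 pair a Week 8–10 H-Score change with tumour change from Screening, while the section's own text takes both from baseline

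*SAP*

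**What the plan says.** **Text of SAP 11.2.2.1.** If data allow, the analysis may examine "potential relationships between decrease from baseline H-score from tumor biopsies, and tumor response". The tumour side is fixed by "Tumor response will be quantified using change from baseline of tumor measurements", expressed as percent change in the sum of lesion diameters (%SLD). The measure is given as "Correlation between decrease in H-score and %SLD will be evaluated using Spearman's correlation coefficient".

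**Meaning of baseline.** SAP 9.2.7 uses the last non-missing value before first dose: Screening for lesion and disease assessments, Day 1 for the tumour biopsy. This applies to every arm. No Week 8 reference for SLD is defined.

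**Displays.** Table 5.0100 is titled "Correlation of Changes in H-Score after Two Weeks of Combo Therapy and Changes in Tumor Burden", and Figure 15.0030 "Scatter plot for Correlation between Changes in H-Score after Two Weeks of Combo Therapy and Changes in Tumor Burden". Mock-up HScore6 has one row for each of the three arms, all with the same tumour marker. Mock-up HScore9 is labelled with the dabrafenib-first arm.

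**Timing in Arms A and B.** SAP 11.2 says "Patients from arm A and arm B will be given combination therapy starting from week 9 after completion of 8 weeks of monotherapy", and SAP 11.2.1 summarises H-Score change from baseline to Week 2 in Arm C but "for change from 8-week and 10-week in Arms A and B for p-ERK using H-score values".

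**Scans.** Protocol Table 19, footnote 6, says "The Week 8 assessment for patients in arms A & B should be done before starting the combination treatment". Scans follow every 8 weeks, and SAP 4.2 places the final analysis after the last patient's Week 16 assessment. SAP 11.2.2.1 does not name the post-baseline scan that supplies %SLD.

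**The concern.** Read as displayed, the two variables in Arms A and B cover different periods. The H-Score change starts at Week 8, while the tumour change starts at Screening. Whatever the tumour did during monotherapy is already in %SLD before the H-Score change begins, so a marker measured over Weeks 8–10 cannot predict it.

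This has two possible effects. Prior shrinkage unrelated to the later H-Score change acts as noise and pulls the coefficient towards zero. Prior shrinkage that is related to it adds bias; for example, patients already well suppressed at Week 8 may have little H-Score left to lose.

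In Arm C both variables start before treatment, so HScore6 would print three coefficients under one label that do not measure the same thing. At stake is the interpretation of an exploratory display, not a primary result.

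**Working it through.** **1. The plan's own figures.** The documents give no figure for this correlation. The only relevant number is the planned 15 patients per arm (SAP 5.1). The half-width stated there reproduces: t(0.975, 14) × 30/√15 = 16.61. The point does not depend on it.

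**2. Windows side by side.**

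| | H-Score change | %SLD |
|---|---|---|
| 11.2.2.1 text, all arms | from Day 1 | from Screening |
| Displays, Arm C | Day 1 to Week 2 | from Screening |
| Displays, Arms A and B | Week 8 to Week 10 | from Screening |

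Only the last row is mismatched. If the unnamed scan is Week 16, about 8 of the 16 on-treatment weeks precede the H-Score change. If it is Week 8, all of them do.

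**3. Size, as an illustration.** Let X be the Week 8–10 H-Score fall, S1 the shrinkage before Week 8, and S2 the shrinkage after it. Write k = SD(S1)/SD(S2), ρ1 = corr(X, S1) and ρ2 = corr(X, S2). With S1 and S2 additive and mutually independent,

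corr(X, S1 + S2) = (ρ2 + kρ1)/√(1 + k²).

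The values of ρ1, ρ2 and k below are assumptions; the documents give none.

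| | k = 0.5 | k = 1 | k = 2 | k = 3 |
|---|---|---|---|---|
| ρ2 = 0.5, ρ1 = 0 | 0.45 | 0.35 | 0.22 | 0.16 |
| ρ2 = 0.5, ρ1 = −0.3 | 0.31 | 0.14 | −0.04 | −0.13 |
| ρ2 = 0, ρ1 = −0.3 | −0.13 | −0.21 | −0.27 | −0.28 |

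Examples: 0.5/√1.25 = 0.45; 0.5/√10 = 0.16; (0.5 − 0.9)/√10 = −0.13.

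The first row is dilution alone. The second and third need a negative relation between prior shrinkage and the later H-Score fall. A tumour variable that starts at the pre-combination scan would target ρ2 in every column.

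The formula is for Pearson correlation on an additive scale. The SAP uses Spearman, and percent change from Week 8 has a different denominator from percent change from Screening, so the table shows direction and rough size only.

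**4. Precision.** With n = 15 and an observed Spearman coefficient of 0.5, the approximate 95% interval on the Fisher scale is tanh(0.549 ± 1.96 × √(1.125/12)), or −0.05 to 0.82.

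**The case against.** The strongest reply is that the governing text contains no mismatch. SAP 11.2.2.1 takes the H-Score decrease from baseline and the tumour change from baseline. A reader might infer that the SAP firmly specifies mismatched windows, but the documents do not support that. The mismatch arises only when the display titles and SAP 11.2.1 are followed instead of the text. What is certain is that text and displays conflict. This part of the reply stands, and it makes reconciliation the first step.

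A reader might also infer that the analysis is meant to show that adding the second drug lowers p-ERK and thereby shrinks tumours. SAP 11.2.2 states a narrower aim, p-ERK's potential as a predictive biomarker, with no causal claim. The alignment problem does not need the causal reading, because a predictor should be set against response that follows it.

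Other points stand in part:

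- The dilution is small when prior shrinkage varies less than later shrinkage (0.45 against 0.5 at k = 0.5), and the documents do not say which case applies.
- A Week 8 reference brings its own difficulties. Patients who progress on monotherapy may switch before eight weeks, percent change is undefined when SLD is 0 at the reference scan, and the Arm A and B rows would use a different reference from Arm C.
- The analysis is conditional on data availability, the study is descriptive, and about 15 patients per arm give little precision under either reference.

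These points limit the importance and shape the rules needed. They do not justify leaving the conflict unresolved.

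**Conclusion.** The point holds in limited form. SAP 11.2.2.1 and its displays disagree about the H-Score window. Following the displays would mix pre-combination tumour change into the Arm A and B coefficients; Arm C is unaffected.

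Under independence, the illustrative loss is from 0.5 to between 0.45 and 0.16 for SD ratios of 0.5 to 3. All of these inputs are assumed.

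A reader might infer that the correlation will change sign. The documents do not support that. Independence alone cannot produce it, and in the working it appears only with an assumed ρ1 of −0.3 and k of 2 or more when the true relation is 0.5. Bias is possible, but its direction and size are unknown.

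This is a cheap improvement to an exploratory analysis. The primary endpoint, ORR and safety are unaffected.

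**What to change.** Amend SAP 11.2.2.1 and its displays so that both variables share a window:

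1. State which H-Score change is used in each arm, and make the text agree with Table 5.0100, Figure 15.0030, HScore6 and HScore9.
2. For the Week 8–10 H-Score change in Arms A and B, compute %SLD from the last scan before combination starts (normally Week 8) to a named next scan, for example Week 16.
3. Treat patients as non-evaluable for this display if they have no on-treatment scan before combination, or an SLD of 0 at that scan. Report how many there are. State how patients who switch early are handled.
4. Keep %SLD from study baseline for Arm C and for any baseline-to-Week 2 H-Score change. It may also be shown for Arms A and B as a supplement.
5. Label the differing reference in HScore6 so that the Arm A and B rows are not read as directly comparable with Arm C.

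The cost is SAP wording, one derived variable with its evaluability rules, and display labels. No new scans, biopsies or visits are needed. The downside is a few non-evaluable patients and the differing reference between arms.

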11.2.2.2. Baseline

Depending upon data availability, exploratory analyses may be performed to examine potential relationships between baseline of H-score from tumor biopsies, and tumor response.

Tumor response will be quantified using change from baseline of tumor measurements (%SLD). Correlation matrices of baseline p-ERK H-Score and %SLD will be reported (Spearman's R, N, and p-value). A scatter plot will be created for each treatment arm.

Summaries of the relationship between baseline H-score and CR/PR/SD/PD (without confirmation) will be assessed if data permit (i.e. if there are enough subjects with CR, PR etc.).

12. SAFETY ANALYSES

Safety data will be summarized and listed by, or under the direct auspices of, the Discovery Biometrics Programmer and reviewed by the Discovery Biometrics Statistician, GlaxoSmithKline. Select safety data will be presented graphically.

Unless otherwise specified, all the safety analyses will be based on the Safety population as defined in Section 6 and summaries will include all events or assessments collected during the study. All the analyses will be performed by treatment arm.

The lists of displays for safety analyses, including population to use for each display, are shown in Section 18.1.3 of the RAP.

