2.1.2. Secondary Objectives

- To evaluate the clinical response.
- To characterize the safety profile of dabrafenib and trametinib in monotherapy and/or in combination including incidences of squamous cell carcinoma (SCC) and other proliferative cutaneous lesions as well as the papulo-pustular rash.
- To evaluate dabrafenib, trametinib, and combination exposures in connection to clinical response and toxicity.

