6. ANALYSIS POPULATIONS

The **Intent-to-Treat Population (ITT)** will consist of all randomized patients whether or not randomized treatment was administered. This population will be based on the treatment to which the patient was randomized and will be the primary population for the analysis of efficacy data. Any patient who receives a treatment randomization number will be considered to have been randomized.

The **Safety Population** will consist of all patients who received at least one dose of randomized treatment and will be based on the actual treatment received. This population will be used for the analysis of clinical safety data.

The **Biomarker Population** will consist of all patients with biopsy performed at screening and at least once during treatment.

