7. TREATMENT COMPARISONS

This is a descriptive study and there will be no treatment comparison. Biomarker, efficacy and safety endpoints will be evaluated for each treatment arm.

Depending on the treatment arm, the treatment descriptor will either be listed as **GSK2118436 BID 8W then GSK1120212 QD + GSK2118436 BID** for Arm A, **GSK1120212 QD 8W then GSK1120212 QD + GSK2118436 BID** for Arm B, or **GSK1120212 QD+ GSK2118436 BID** for Arm C.

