9.3.1. Time in relation to treatment

Adverse events, serious adverse events, death, laboratory data, vitals, ECG, ECHO/Multiple gated acquisition scan (MUGA), and questionnaire data (ECOG, FACIT-F, FKSI-19, SQLQ, CTSQ, MRU, and KPS), will be assigned to the study time periods defined below. Partial dates will be imputed into full dates, if applicable, for slotting data to the appropriate categories below (see Section 9.2.5). Flag variables (ATTYPCD/ATTYPER) indicating the study time periods will be added to these datasets.

Pre-therapy is defined as the time prior to the subject's first dose of study treatment.

On-therapy is defined as the time from first dose of study treatment to the last dose date of study treatment.

Post-therapy is defined as any time beyond the on-therapy period.

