18.1.3. Safety (Section 3)

18.1.3.1. Tables

Table No.	Title	Population	Component / Therapeutic Area (hyperlinked to IDSL LN DB)	IDSL No. or Example Shell No.	Study-Specific Display Notes	Deliverable Priority
3.0010	Summary of Exposure to Dabrafenib	Safety	Exposure Displays/ Oncology Core/	OEX1		SAC
3.0011	Summary of Exposure to Trametinib	Safety	Exposure Displays/ Oncology Core/	OEX1		SAC
3.0040	Summary of Dose Reductions	Safety	Dose Modifications Displays/ Oncology Core/	ODMOD1		SAC
3.0041	Summary of Dose Interruptions	Safety	Dose Modifications Displays/ Oncology Core/	ODMOD2		SAC
3.0044	Summary of Dose Escalations	Safety	Dose Modifications Displays/ Oncology Core/	ODMOD8		SAC
3.1010	Adverse Event Overview	Safety	Adverse Events Displays/ Core/	AE13		SAC
3.1020	Summary of All Adverse Events	Safety	Adverse Events Displays/ Core/	AE1	Displayed by SOC and PT, and sorted in descending order (for all patients). Have 4 columns (1 for each treatment arm + total).	SAC
3.1030	Summary of Frequent Adverse Events	Safety	Adverse Events Displays/ Core/	AE3		SAC
3.1040	Summary of Common Non-Serious Adverse Events	Safety	Adverse Events Displays/ Core/	AE1		SAC

CONFIDENTIAL

BRF116613

Table No.	Title	Population	Component / Therapeutic Area (hyperlinked to IDSL LN DB)	IDSL No. or Example Shell No.	Study-Specific Display Notes	Deliverable Priority
3.1041	Summary of Non-Serious Adverse Events by Preferred Term with Occurrences \geq 5%	Safety	t_ae_non_ser.rtf		See Mock-Up/	SAC
3.1070	Summary of Adverse Events By Maximum Grade by Preferred Term	Safety	Adverse Events Displays/ Oncology Core/	OAE7		SAC
3.1071	Summary of Adverse Events By Maximum Grade by System Organ Class and Preferred Term	Safety	Adverse Events Displays/ Oncology Core/	OAE1		SAC
3.1110	Summary of Adverse Events Related to Study Treatment	Safety	Adverse Events Displays/ Core/	AE1		SAC
3.1120	Summary of Adverse Events Related to Study Treatment by Maximum Grade	Safety	Adverse Events Displays/ Oncology Core/	OAE7		SAC
3.1210	Summary of Serious Adverse Events by Preferred Term	Safety	Adverse Events Displays/ Core/	AE3		SAC
3.1211	Summary of Serious Adverse Events by Preferred Term by System Organ Class and Preferred Term	Safety	Adverse Events Displays/ Core/	AE1		SAC
3.1310	Summary of Serious Adverse Events Related to Study Treatment by Preferred Term	Safety	Adverse Events Displays/ Core/	AE3		SAC

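### General AE and SAE tables and worst-case laboratory and LVEF tables merge monotherapy with combination in Arms A and B, so the by-regimen safety objective is only partly met

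*SAP*

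**What the plan says.** The secondary safety objective in SAP 2.1.2 (and protocol Section 2) is "To characterize the safety profile of dabrafenib and trametinib in monotherapy and/or in combination including incidences of squamous cell carcinoma", with other proliferative skin lesions and papulo-pustular rash also named.

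The rules for the displays are these:

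- SAP 12: "summaries will include all events or assessments collected during the study", and "All the analyses will be performed by treatment arm".
- SAP 6: the Safety Population "will be based on the actual treatment received. This population will be used for the analysis of clinical safety data". Under SAP 9.2.10 a patient changes arm only if the treatment taken differed from the assigned one throughout.
- SAP 7: one label covers the whole sequence. Arm A, for example, is "GSK2118436 BID 8W then GSK1120212 QD + GSK2118436 BID".
- SAP 9.3.1: "On-therapy is defined as the time from first dose of study treatment to the last dose date of study treatment". The only other periods are before and after therapy.
- SAP 18.1.3.1, note to Table 3.1020 (all AEs): "Have 4 columns (1 for each treatment arm + total".

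There are two exceptions. SAP 12.3 tabulates AESIs separately for dabrafenib monotherapy, trametinib monotherapy and the combination. SAP 12.7 and 12.8 also summarise laboratory values and grades, vital signs, ECOG status and ECG findings by scheduled visit.

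**The concern.** Arms A and B are designed to contain two regimens, and the objective asks about safety on each. A general AE table by arm counts a patient once per preferred term at the worst grade seen at any time. An event in Week 3 on one drug and an event in Month 6 on two drugs therefore fall in the same cell. A reader of the study report could then not say how often any AE, any serious AE, any related AE or any grade 3 or 4 AE occurred on dabrafenib alone, on trametinib alone, or on the combination after monotherapy.

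There is a second, more practical gap. The AESI tables need each event assigned to a regimen, and SAP 9.3.1 gives no rule for doing so. Nominal week cannot stand in for one, because SAP 3 lets patients who progress on monotherapy move to the combination before Week 8.

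**Working it through.** The plan states no figure on this point, so there is nothing to reproduce. The check is structural, with two illustrations of size.

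**Step 1: which displays separate the regimens in Arms A and B?**

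| Display | Source | Split by regimen? |
|---|---|---|
| AE overview, all AEs, maximum grade | SAP 12.2; Tables 3.1010, 3.1020, 3.1070 | No: by arm, once per patient |
| Related AEs | SAP 12.2; Table 3.1110 | No: by arm |
| SAEs | SAP 12.4; Table 3.1210 | No: by arm |
| Maximum-grade and worst-case laboratory | SAP 12.7 | No: one worst value per patient |
| LVEF change | SAP 12.8; Table 3.4090 | No: worst post-baseline value only |
| Laboratory, vital signs, ECOG, ECG by visit | SAP 12.7, 12.8 | Approximately |
| AESIs | SAP 12.3; Tables 3.1600 to 3.1811 | Yes, but with no assignment rule |

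The by-visit split is approximate because visits carry a window of 7 days either side (protocol Section 3) and some patients switch early. With chemistry and haematology every 4 weeks (protocol Table 19), Weeks 4 and 8 are broadly monotherapy, and Week 12 onward is combination.

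**Step 2: how many patients are affected?** With 54 patients randomised 1:1:1 there are 54 / 3 = 18 per arm, so Arms A and B together hold 36 of 54.

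**Step 3: how much exposure is merged?** For a patient who completes the 8 weeks, the monotherapy share is 8 / (weeks on treatment):

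- 16 weeks, the time of the last patient's efficacy assessment that triggers the final analysis (SAP 4.2): 8 / 16 = 50%.
- 24 weeks (assumed): 8 / 24 = 33%.
- 10.7 months, the median time on treatment in the earlier combination study (protocol 1.1.3, taken as an assumption): 10.7 × 30.4375 / 7 = 46.5 weeks, and 8 / 46.5 = 17%.

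**Step 4: what does a merged incidence tell the reader?** Fatigue is not on the AESI lists in SAP 12.3. The inputs are *a* = 26% on trametinib (protocol 1.1.2) and *b* = 37% on the combination (protocol 1.1.3). They come from different trials with different follow-up, so this is illustration only. The proportion of Arm B with fatigue at any time would be:

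- nested (every patient affected in the first phase is affected again in the second): max(*a*, *b*) = 37%, or 0.37 × 18 = 6.7 patients;
- independent: 1 − (1 − 0.26)(1 − 0.37) = 1 − 0.74 × 0.63 = 53%, or 9.6 patients;
- disjoint: 0.26 + 0.37 = 63%, or 11.3 patients.

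The same two rates give anything from about 7 to 11 of 18 patients. In reverse, a reported 53% is compatible with any monotherapy rate from 0% to 53%, so neither phase rate can be recovered.

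**The case against.** The strongest reply is that the objective is largely served already. It names squamous cell carcinoma, proliferative skin lesions and rash. The AESI tables cover cuSCC/keratoacanthoma, skin toxicity, cardiac, hepatic and ocular events and more, by regimen and by grade. This stands for those categories. It does not reach general AEs, related AEs or SAEs. The lists also differ by regimen: rash is on the trametinib and combination lists but not on the dabrafenib one, although all three lists are expressly open to additions.

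Four stronger readings are tempting, and the documents do not support them.

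- A reader might infer that every safety table outside the AESIs is affected. By-visit laboratory, vital-sign, ECOG and ECG summaries are not, and SAP 12.1 reports exposure separately for each drug.
- A reader might infer that the tables follow the randomised arm. They follow actual treatment. The merging is the same either way.
- A reader might infer that Arms A and B cannot be set beside upfront combination. They can. The arms are whole sequences, SAP 2.3 speaks of treatment sequence, and the by-arm tables show the sequences side by side. SAP 7 also plans no treatment comparison.
- A reader might illustrate the harm with pyrexia (28% on dabrafenib, 52% on the combination in the protocol's background). Pyrexia is an AESI on both of those lists, so it is already reported by regimen.

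Two cautions about a remedy also stand. Cells of at most about 18 patients, spread over many preferred terms, are thin. ECHO is scheduled at Week 4 and then every 12 weeks (protocol Table 19), so LVEF on monotherapy would rest on one scheduled reading.

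**Conclusion.** The point holds for the AE overview, all-AE, maximum-grade, related-AE and SAE tables, the maximum-grade and worst-case laboratory tables, and worst-case LVEF. In about 36 of 54 patients these mix two regimens, and the general AE and SAE part of the secondary objective cannot be read from any planned table. It does not follow that the whole objective fails: the AESI displays meet a substantial part of it, and the by-visit summaries meet a little more.

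The missing assignment rule matters independently, because the AESI tables already planned depend on it. The combination AESI group also takes in both upfront and post-monotherapy patients, with no stated split between them.

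This concerns description in a descriptive trial, and the primary endpoint is untouched. The fatigue range rests on rates from other trials. The exposure shares assume a full eight weeks of monotherapy. The structural conclusion depends on neither. The change should be made because it answers a stated objective from data already collected.

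**What to change.** **Define periods in SAP 9.3.1 from actual dosing dates:**

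- initial monotherapy: first dose to the day before the first combination dose;
- combination: first combination dose until either drug is permanently discontinued, or last dose;
- any later single-drug period, kept separate. It is needed because SAP 9.1 and protocol 4.2.1 allow a patient to continue on one drug after the other is stopped, which would otherwise mix regimens again, in Arm C too.

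The existing pre- and post-therapy categories remain. Assign each event by onset date, and count a worsening in grade after the switch in the combination period. SAP 9.2.5 can set a missing onset day to the first of the month, which would place an event before a mid-month switch, so state how such events are handled.

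**Use the flag in the displays.** Apply it to the AESI tables. Repeat Tables 3.1010, 3.1020, 3.1070, 3.1110, 3.1210, the maximum-grade laboratory tables and the LVEF table by arm and period (A-mono, A-combo, B-mono, B-combo, C), with the number of patients entering each period as denominator and the exposure time in that period.

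**Keep the by-arm tables,** and label the period displays descriptive: combination-phase patients in Arms A and B are a post-randomisation subset, namely those who reached the combination.

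**Cost:** one derived variable and extra columns, with no new data collection. The price is small cells and few scheduled ECHOs during monotherapy.
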